12.2. Reporting of Adverse Events

Clinical information on AEs (as defined above), their presentation, date of event, management, relationship and outcome must be reported on a CRF and sent to Medtronic. Subjects with ongoing AEs at the time of the prospective visit may not exit the study until the AE has been resolved or is determined not able to be resolved. As this is a post-market study of a marketed device the sponsor and investigator will comply with regulations on event reporting according to the Medical Device Reporting System (MDR). The designated study personnel will have two opportunities to collect AE's for each subject:

At the retrospective data collection of Sophono implantation and post-implantation, any surgical procedure or device related AE will be recorded on the applicable CRF. This data collection may occur at any time after the subject consents to the study. No safety reporting to IRBs will be required for retrospective events.

At the follow-up visit, the designated study personnel will examine and query the subject on the experience of any AEs, and designated study personnel will record data on the applicable CRF. This data collection may occur at any time after the subject consents to the study. These prospective observed events will be reported to IRBs or other committees according to the rules and timeframe of the governing site or IRB.

No AEs will be collected after the subject exits the study.

13. Statistical Design and Methods

13.1. Sample size

Since the primary endpoint is composed of a safety and efficacy endpoint, the sample was determined by the primary objective on safety because it requires the larger sample size. An approximate total of 100 subjects will be enrolled.

Sample size on safety

The sample size calculation was estimated using data from previous studies with a precision-based calculation. (20, 21) Recent data have shown that 15.2% of percutaneous implants are lost in children and adverse skin reactions were found in 7.8 % during follow-up visits. (21) Using this information and assuming a lower incidence of implant loss in transcutaneous devices (19, 22, 23) and a lower incidence of skin reaction (18, 24), a minimum incidence of 14% of any adverse events with a sample size of 72 subjects will be able to obtain a 95% confidence level with a precision of +/- 9% (ranging from 5% to 23%). Considering a 25% withdrawal or potential dropout rate, a total of approximately 100 subjects will be enrolled.

Sample size on efficacy

It is expected that at least 6 paired subjects with the pure tone audiometry evaluation will be needed in order to demonstrate a difference in means between unaided and aided measurements in Hearing Improvement measured as PTA. From a literature search we found that studies have shown an average of 50% improvement on hearing measured as PTA.(13, 20, 21, 25-34) In the paper of Siegert (34) the mean and standard deviation of pure tone audiometry in 21 patients was 58.7 ± 8.2 dB HL unaided and 29.7 ± 8.2 dB HL aided. Based on these values, alpha level 5%, power 95% and two-sided test, a total of 6 paired subjects are needed.

13.2. Data analysis and reporting

A detailed description of the statistical methods will be contained in the Statistical Analysis Plan. Any change to the data analysis methods described in this section and/or the Statistical Analysis Plan will require an amendment only if it changes a principal feature of the study description. Any other changes to the data analysis methods will be described and justified in the Final Report or publication.

It is anticipated that SAS (SAS Institute Inc., Cary, NC, USA) will be used to perform all statistical analyses. Statistical tests will be based on a two-sided significance level of 0.05. No adjustments for

This document is electronically controlled. Printed copies are considered uncontrolled.

Confidential

multiple comparisons will be performed. Since the impact of missing data is expected to be small no multiple imputation method for missing data is planned. However, should the issue of missing data arise, the choice of the imputation method for missing data will depend on the pattern of missing data and the type of the imputed variable.

The study is a multicenter trial and a multicenter impact on primary outcome will be investigated. A description on primary outcome by sites will be provided.

Outliers and influential observations will be identified via graphical plots. Once outliers or influential observations are identified, the study team will be informed and according to their decision the analysis for primary endpoint may be repeated excluding the outliers. Additional exploratory analyses will be conducted as deemed appropriate.

Descriptive statistics will be used to summarize patient characteristics. For categorical variables, the minimum description will consist of the sample size, numbers of missing data and valid data, the frequency and the percentage of each category. Denominators for calculation of percentages will be taken as the number of subjects with available (not missing or unknown) observations in the specified patients sets and groups unless otherwise stated. Percentages will be presented with no decimal. For continuous variables, the description will consist at least of the sample size (N), number of subjects with non-missing observation (n), mean, standard deviation, standard error, minimum, median and maximum. For $n < 3$, only mean, minimum and maximum will be displayed. In general, minimums and maximums will be presented to the same level of accuracy as the raw data; means and medians will be presented to 1 further decimal place; if appropriate, standard deviation and standard error will be presented to 2 further decimal places.

The primary analysis is based on safety and effectiveness.

13.3. Safety endpoint

Event rates, weighted for center, will be displayed together with their 95% confidence interval (95%CI); for each possible sub-group, analyses will be compared by means of a mixed Poisson model, with center included as random effect. In the presence of over dispersion, negative binomial regression will be used. Over dispersion will be assessed both with a goodness-of-fit test and a likelihood ratio test for $\alpha=0$. The incidence rate ratio (IRR) and 95%CI will be reported [IRR=rate group1 / rate group2]. The exposure time (days/months) will be computed from implantation to the date of the follow-up visit for each patient [(data end – data in)/30.4].

Specific events will be analyzed using survival analysis. The analysis will be supported by a Kaplan Meier curve indicating the number of patients at risk and comparison of curves will be done using the generalized Log-Rank Test where appropriate. The exposure time (months) will be computed from the date of the implantation to the date of the last available follow-up or date of event: [(data end – data in)/30.4].

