9.3. Inclusion Criteria

- Any subject who currently has or who has had the Sophono implant (including those who have been explanted)
- Has or has had Sophono implant for 3 months or longer

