10.1. Schedule of Events

After proper administration and signing of the IC and Research Authorization Forms, all potential subjects will be assessed for study eligibility based on the Inclusion and Exclusion Criteria. Inclusion and Exclusions data as well as limited demographic information will be captured in the subject CRFs.

A ***retrospective review*** of the subject's medical chart will be performed to gather and report data on subject surgical history, reportable AEs from the time of implantation to time of chart review, previous QOL scores, and previous audiometric testing results for Alpha 2 and/or Alpha 2 MPO processors.

An ***in-office visit*** will be conducted with an ENT physician and Audiologist, ideally on the same day, where the following assessments will take place:

ENT Visit:

The ENT visit will consist of an examination of the ear and implant site for skin complications (according to the *Holger Skin Evaluation Index* in Table 2) or other potential AEs (see Section 12 for reportable AEs). The ENT Visit CRF will detail findings (such as erythema, scar, etc.) as well as complications (skin loss, infection, etc.). Any such complications will be recorded on an AE form.

Sophono system satisfaction and QOL questions shall also be administered to allow the subjects' perceived benefits to be assessed. The QOL assessment will be done using the APHAB Version A.

Table 2. Holger Skin Evaluation Index

The skin directly over the implant site will be evaluated on the Holger Skin Evaluation Index.

Holger Skin Evaluation Index
0 = No irritation. Epithelium debris removed if present.
1 = Slight redness, local treatment.
2 = Red and slightly moist tissue. No granuloma formation noted. Local treatment. Extra controls.
3 = Status as in 1 and 2 but local revision became necessary.
4 = Removal of skin-penetrating implant necessary due to infection.
R = Removed implant for reasons not related to skin problems.

Audiology Visit:

All audiometric testing equipment should be calibrated and tested to American National Standards Institute (ANSI) standards, in good repair and functioning well.

All tests should be performed in the order presented in Table 3. Subject will be blinded to processor order.

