An anticipated adverse event is defined as an AE, the nature, severity, or degree of incidence of which is known and identified in applicable product labeling, published literature or the Investigational Plan or Informed Consent.

Based on event reports through literature review (15-19) anticipated Surgical Related AE's possibly noted in the Operative Report during the retrospective medical chart review should be reported on the appropriate CRF. These events may include:

This document is electronically controlled. Printed copies are considered uncontrolled.

Confidential

Table 4. Surgical Related Adverse Events

Event
Excessive Bleeding
Rupture of Dura
Cerebrospinal Fluid (CSF) Leak
Anesthesia Related Complications

Anticipated Post-operative Related AE's possibly seen in the retrospective medical chart review or at the office visit and their reportability within the study may include:

Table 5. Post-Operative Related Adverse Events

Event	Reportable Criteria
Abscess	Requiring medical intervention
Bleeding	Requiring medical intervention
Dehiscence (at Incision Site)	Requiring medical intervention
Depilation (Loss of Hair at Implant Site)	Excessive or cosmetically bothersome
Hematoma	Requiring medical intervention
Hyperemia	Excessive or requiring medical intervention
Infection (i.e. Cellulitis, Bacterial, etc.)	Requiring medical intervention
Inflammation/Skin Irritation (Redness)	Holger 2, 3, 4
Numbness (Hypoesthesia)	Notable or bothersome to subject

This document is electronically controlled. Printed copies are considered uncontrolled.

Confidential

Pain (Local)	Prolonged surgical procedure pain or pain lasting more than 10 days
Pressure (at the Implant Site)	Feeling of pressure continuing after subject begins using the processor
Scarring	Abnormal or Hypertrophic
Skin Necrosis (Pressure)	Requiring medical intervention
Swelling	Continuing after subject begins using the processor

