7.10.1 Primary endpoint

The primary safety endpoint is the proportion of AEs related to the Sophono implant or surgery, which will be assessed through retrospective surgical chart review and prospective ENT exam. The primary safety endpoint will be evaluated on FAS. The AEs used for this endpoint are according to Investigator's determination of the event's relatedness to the device or surgery.

Adverse Event rates will be displayed together with their 95% confidence interval (95%CI) overall, by site and by type of event.

A time to first Adverse Event will be performed using survival analysis. The analysis will be supported by a Kaplan Meier curve indicating the number of patients at risk and any possible comparison of curves between groups will be done using the Log-Rank Test where appropriate.

Table x - Primary safety endpoint – Sophono Implant related Adverse Events rates

Figure x - Kaplan Meier estimate of first Sophono Implant related Adverse Event occurrence

Table x - Kaplan Meier estimate of first Sophono Implant related Adverse Event occurrence

The primary effectiveness endpoint is the absolute difference (gain) in the free-field pure tone audiometry assessed by PTA unaided (AC) and aided by the Alpha 2 MPO processor. The primary effectiveness endpoint will be evaluated on PPS.

The difference between unaided and aided measurements will be analyzed by means of paired (samples) t-test or Wilcoxon signed rank sum test according to the normal or non-normal distribution.

Additional analysis will be performed on:

- the "within indication" subset will exclude from the analysis subjects whose Prospective AC & BC tests do not meet the device indications for use.

- The subsets defined by implanted ear diagnosis. For the subject affected by SSD, analyses will be performed for both the derived variables (both NR substitution methods).

Table x - Primary effectiveness endpoint - Difference in PTA between unaided (AC) and aided by the alpha 2 MPO Processor (Audiogram Results Gain)

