7.13 Changes to Planned Analysis

The analysis described in the CIP could differ from that presented in this SAP due to data availability.

Any possible comparison of Adverse Event rates will be compared by means of a mixed Poisson model. In the presence of over dispersion, negative binomial regression will be used. Over dispersion will be assessed both with a goodness-of-fit test and a likelihood ratio test for $\alpha=0$. The incidence rate ratio (IRR) and 95%CI will be reported [IRR=rate group1 / rate group2].

Any specific events will be analyzed using survival analysis. The analysis will be supported by a Kaplan Meier curve indicating the number of patients at risk and comparison of curves will be done using the generalized Log-Rank Test where appropriate.

8 Validation Requirements

All collected data will be reviewed for completeness, correctness and consistency. In case of issues, queries will be sent to the investigator to complete, correct or comment on the data. To ensure the quality of the results provided for the study in the form of tables, listings and figures, and the derived datasets the following processes are used:

- Statistical programming and analysis will be done by qualified programmer(s) and statistician(s) following applicable procedures and best practices.
- The derived datasets will be validated by a second programmer or statistician.
- The tables will be validated by a second programmer or statistician.
- Statistical results will be reviewed and confirmed by a second statistician.

The entire set of tables, listings, and figures (TLF) will be 100% checked for accuracy, completeness, and consistency prior to inclusion in the interim or final clinical study report. According to Medtronic SOPs the level II validation (the peer reviewer reviews the code; where appropriate, performs manual calculations or simple programming checks to verify the output) will be implemented for both Datasets and TLFs.

9 References

1. <http://www.strobe-statement.org/index.php?id=available-checklists>

10 Statistical Appendices

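### AE rates and rate ratios per month since implantation (Protocol 13.3) can be strongly confounded by length of follow-up

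*Protocol*

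**What the plan says.** **Rate model.** Protocol 13.3 displays event rates, weighted for center, with 95% CIs. For each possible sub-group, "analyses will be compared by means of a mixed Poisson model, with center included as random effect", with negative binomial regression if the counts are overdispersed. The effect measure is the IRR, the ratio of two groups' rates, with its 95% CI. The same paragraph fixes the time base: "The exposure time (days/months) will be computed from implantation to the date of the follow-up visit for each patient". A second paragraph plans Kaplan-Meier curves and log-rank tests for specific events, with time running from implantation to the event or last follow-up.

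**Follow-up.** Protocol 9.3 requires "Has or has had Sophono implant for 3 months or longer" and sets no upper limit. Protocol 10.1 has the chart review collect "reportable AEs from the time of implantation to time of chart review", so the window differs by subject.

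**Events.** Protocol 10.6 and 12.2 collect procedure-related as well as device-related AEs. Protocol 12.1.1 contains "Table 4. Surgical Related Adverse Events", which lists bleeding, dural rupture, CSF leak and anesthesia complications. Table 5 mixes events tied to the operation (incision-site dehiscence, prolonged surgical pain) with events tied to processor use (pressure or swelling that persists once the processor is worn).

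**SAP.** Section 7.10.1 states: "The primary safety endpoint is the proportion of AEs related to the Sophono implant or surgery". It shows AE rates overall, by site and by event type without naming a denominator, and adds a Kaplan-Meier analysis of time to first AE. Section 7.13 states: "Any possible comparison of Adverse Event rates will be compared by means of a mixed Poisson model". It keeps the negative binomial fallback and the IRR but names no groups, exposure or offset. Section 7.6 derives time to first AE as the study evaluation date minus the first AE date.

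Neither document separates operative from later AEs in the rate model.

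**The concern.** Dividing a count by months since implantation describes risk properly only if events accrue at a roughly constant rate. An operative event is attached to the procedure. It can happen only on day zero, and each further month of follow-up adds to the denominator but cannot add to the numerator. Surgery-linked wound events behave similarly. The more of the AE burden that is early, the more the rate depends on how long ago the cohort was implanted.

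Two things follow. The overall rate falls as the cohort ages, with no change in safety. And two sub-groups with the same risk at every time after surgery get different rates if one was implanted earlier, so the IRR shows a difference that does not exist. The negative binomial fallback does not help: it handles extra variation between subjects, not a rate that changes with time.

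Unequal follow-up is plausible, though not documented. Protocol 5.1 describes processors released as successive upgrades since 2010, so a split by processor could track implant date, and sites may have started implanting at different times. Safety of the implant is one of the two primary objectives, so a diluted rate or a false sub-group signal would matter.

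**Working it through.** **1. The plan's own safety figure.** The only one stated is for a proportion: 14% incidence, 72 subjects, ±9% (5% to 23%).

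- Wald half-width: 1.96 × √(0.14 × 0.86 / 72) = 0.080.
- With continuity correction 1/(2 × 72) = 0.007: 0.087, giving 5.3% to 22.7%, which rounds to the stated range.
- Dropout: 72 / (1 − 0.25) = 96, about 100.

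The figure reproduces. No person-time rate or IRR is stated, so there is none to reproduce.

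**2. Expected rate under identical risk.** Let *E* be early events per subject, *h* a constant later rate per month, and *T* mean follow-up in months. Then rate(*T*) = (*E* + *hT*) / *T*.

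Assumptions: 0.14 AEs per subject by 24 months (borrowing the planned 14%), of which a share *f* is early. So *E* = 0.14*f* and *h* = 0.14(1 − *f*)/24. Both groups share the same process, so the true ratio is 1.

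Example, *f* = 0.5: *E* = 0.07 and *h* = 0.07/24.
- 12 months: (0.07 + 0.035)/12 = 0.00875 per month.
- 36 months: (0.07 + 0.105)/36 = 0.00486 per month.
- IRR = 1.80.

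| Early share *f* | IRR, 12 vs 36 mo | IRR, 12 vs 24 mo | IRR, 24 vs 36 mo |
|---|---|---|---|
| 0 | 1.00 | 1.00 | 1.00 |
| 0.25 | 1.36 | 1.25 | 1.09 |
| 0.5 | 1.80 | 1.50 | 1.20 |
| 0.75 | 2.33 | 1.75 | 1.33 |
| 1 | 3.00 | 2.00 | 1.50 |

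When all AEs are early, the IRR is simply the inverse ratio of the follow-up times.

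**3. Overall rate, per person-year.**

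| Early share *f* | 3 mo | 12 mo | 60 mo |
|---|---|---|---|
| 0 | 0.070 | 0.070 | 0.070 |
| 0.5 | 0.315 | 0.105 | 0.049 |
| 1 | 0.560 | 0.140 | 0.028 |

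**4. False positives.** Simulation of a two-group Poisson rate-ratio Wald test at the two-sided 5% level: 50 subjects per group, the same AE process in both, up to 3,000 runs, no center effect, runs with no events in a group dropped.

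| Early share *f* | Follow-up 3–21 vs 24–48 mo | Both groups 3–48 mo |
|---|---|---|
| 0 | 3% | 4% |
| 0.5 | 20% | 3% |
| 0.75 | 35% | 4% |
| 1 | 53% | 4% |

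**5. Time to first AE as derived in SAP 7.6.** Take a subject with an operative AE who is evaluated at month 36. The true time is 0, but evaluation minus AE date gives 36 months. A first AE found at that visit has a true time of 36 months and gets 0. The order is reversed, and it departs from the definition in Protocol 13.3, which runs from implantation.

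**The case against.** **The primary safety endpoint is a proportion.** Both documents define it so, and the sample size rests on one. The SAP's rates may be those proportions. A reader might infer that the primary endpoint itself is a person-time rate; the documents do not say that. This stands. The problem is certain only for the rates and IRRs of Protocol 13.3.

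**SAP 7.13 states no exposure.** A reader might infer that it also divides by months since implantation. It does not say so, and the device exposure in SAP 7.8 is a separate descriptive summary. This stands too, but it leaves the model unspecified.

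**Surgical AEs over person-months needs both documents.** The Protocol defines the endpoint by relation to the implant; the SAP adds surgery but gives no person-time. That is a fair reading of the definitions. However, Protocol 12.2 records surgical AEs, and 13.3 does not exclude them from its rates.

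**The rates need not mainly reflect follow-up.** A reader might infer that they do. That would need a large early share of AEs and, for the IRR, groups whose follow-up differs. The documents give neither, no comparison groups are named, and some Table 5 events arise with continued processor use. With a constant rate there is no bias, and with equal follow-up the IRR is unbiased. For 24 vs 36 months the IRR is only 1.09 to 1.50 even when a quarter or more of AEs are early.

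**Kaplan-Meier and log-rank analyses are planned.** They do not assume a constant rate, and they partly mitigate the problem. They cover first or specific events only, leave the rates and IRRs unchanged, and are unreliable for first AEs while the SAP 7.6 derivation stands. The display by event type would list operative events separately, but it does not take them out of the overall rate or the model.

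**Conclusion.** The concern holds in a limited form. Protocol 13.3 ties AE rates, the Poisson or negative binomial model and the IRR to months since implantation. No offset is written out, but this is the natural reading of its paragraph. Operative events at time zero do not fit that model, and open-ended follow-up from 3 months gives the misfit room to matter. The overall rate and any sub-group IRR can be strongly confounded by length of follow-up.

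The size cannot be determined from the documents. The IRR range of 1.0 to 3.0 for 12 vs 36 months rests on an assumed 0.14 AEs per subject by 24 months, an assumed early share and assumed follow-up times. The primary proportion is not invalidated. The correction is worth making before analysis because safety is a primary objective and the change needs no new data: Protocol 12.1 already requires AE dates.

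**What to change.** In SAP 7.10.1 and 7.13, with the derivation in 7.6:

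1. **Operative AEs (Table 4).** Report them as a proportion per implant procedure with an exact CI, and exclude them from the Poisson, negative binomial and IRR models.
2. **Post-operative AEs.** State the denominator and the offset, including the end date for subjects with no visit (Protocol 7 limits the visit to those still implanted). Base the overall estimate and any group comparison on Kaplan-Meier risk at fixed times from implantation, or on a model with one early/late period split. A crude proportion is not a substitute: with AEs at a constant rate (*f* = 0), expected events per subject rise from 0.14 × 12/24 = 0.07 at 12 months to 0.14 × 36/24 = 0.21 at 36.
3. **Time to first AE.** Define it as AE date minus procedure date, with subjects without an AE censored at last follow-up, in line with Protocol 13.3.

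Do not split the by-site display by period. At 14% of about 100 subjects, some 14 would have an AE; even two periods across up to 15 sites would give 30 cells, most of them empty.

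The cost is slightly wider CIs, a little more programming and a few lines of SAP text.
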